Obesity is the number one and most preventable Type 2 diabetes (T2D) risk factor, yet despite a \$20 billion annual expenditure on diet and weight loss efforts, 87% of US adults are overweight or obese. Racial/ethnic disparities exist, with Non-Hispanic Black adults almost two times more likely than non-Hispanic Whites to have a T2D diagnosis (13.4% and 7.3% respectively). Blacks compared to Whites have a 50% higher morbidity and mortality and are at substantially higher risk of diabetes-related complications such as end stage renal disease and amputations. Evidence-based lifestyle interventions (LIs) to prevent T2D are available and demonstrate that weight loss as small as 5% is clinically meaningful, however 40-60% of intervention participants do not achieve the intervention weight loss goal. The original clinic-based Diabetes Prevention Program (DPP) LI clearly demonstrated that a LI that focused on a 7% weight reduction through changing behavior related to nutrition and increasing moderate intensity physical activity (PA) to 150 minutes weekly reduced incident diabetes by 58% among high-risk adults. The DPP used an intense one-on-one delivery model and included a "toolbox" of personalized strategies for use with individuals who were challenged with reaching the 7% weight loss goal. One on one approaches are not practical for public dissemination, thus upon translation and subsequent national dissemination of the DPP as the National DPP (NDPP), the paradigm has shifted among LIs to a group-based delivery model. Group based delivery is more cost effective than more resource intense one-on-one approaches, but with group-based delivery, all participants receive the same intervention regardless of their weight loss response. This "one size fits all" model is problematic because it does not account for heterogeneity in treatment response among participants. Previous research has translated the DPP to a variety of "real world" settings such as community centers, senior center and military bases to address issues of access and public health. Churches have been among these settings and the effectiveness of church-based health promotion interventions support previous research regarding the importance of providing contextual and culturally adapted interventions to racial/ethnic minority populations. This study seeks to establish the efficacy of identifying weight loss nonresponders early in a Diabetes Prevention Program (DPP) intervention in 20 community settings (primarily churches and community centers) and providing them with individual-level, enhanced treatment through telephone contacts and access to additional resources. We characterize nonresponse as a weight loss of less than or equal to 1% by week four of the intense phase of the intervention. Additionally, we will examine potential mediators and moderators of the relationship between intervention status and weight loss response at 6 months in both nonresponders and responders and lastly we conduct a cost effectiveness analysis to evaluate the cost of the intervention arm by comparing the incremental cost and weight loss with the active control arm. This study addresses key gaps in the literature about the weight loss effects of identifying nonresponders early and characterizing individuals who need more intense personalized strategies. We hypothesize that changes between baseline and 3 months will be more pronounced among the nonresponders in the intervention group compared to the nonresponders in the active control group.

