
## Objectives

List your research objectives. Please include a summary of intended research objectives in the box below.

The objectives of this pilot study are:

- 1) To evaluate differences over time in the primary outcome of weight, and secondary outcomes (i.e., PA level, blood pressure, and dietary behaviors) between nonresponders in the intervention group compared to nonresponders in the active control group.
- 2) To examine potential mediators and moderators of the relationship between intervention status and weight loss response at 6 months in both nonresponders and responders
- 3) Conduct a cost effectiveness analysis to evaluate the cost of the intervention arm by comparing the incremental cost and weight loss with the active control arm

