## Study Design

Describe and explain the study design (e.g., observational, secondary analysis, single/double blind, parallel, crossover, deception, etc.).

- **Clinical Research:** Indicate whether subjects will be randomized and whether subjects will receive any placebo.
- **Community-Based Participatory Research:** If you are conducting [community-based participatory research \(CBPR\)](#), describe strategies for involvement of community members in the design and implementation of the study, and dissemination of results from the study.
- **Qualitative research:** Indicate ranges where flexibility is needed, if a fixed interview transcript is not available, describe interview topics including the most sensitive potential questions.
- **Research Repositories:** If the purpose of this submission is to establish a Research Repository (bank, registry) and the material you plan to collect is already available from a commercial supplier, clinical lab, or established IRB approved research repository, provide scientific justification for establishing an additional repository collecting duplicate material. Describe the repository design and operating procedures. For relevant information to include, see the [UK Research Biospecimen Bank Guidance](#) or the [UK Research Registry Guidance](#).

This study is a two-group cluster randomized design to enroll and follow-up 500 participants over a period of 6 months.

Participants will be randomized by site assigned to:

- 1) DPP-GLB standard intervention (n=250)
- 2) DPP-GLB enhanced intervention (n=250)

We will involve our established Community Advisory Board through all stages of the intervention, from recommending community sites to engage in the project, to assisting with identifying Community Health Workers and reviewing project results prior to publication and presentations.

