### 1) Diabetes Prevention Program Group Lifestyle Balance (DPP-GLB) Intervention Program (standard)

The intervention is based upon the 2017 version of the University of Pittsburgh DPP Group Lifestyle Balance Program (DPP-GLB). The DPP-GLB is a CDC-recognized curriculum and is a direct adaptation of the DPP curriculum for use in the public health arena. The original DPP was developed with Social Cognitive Theory (SCT). SCT is a behavioral theory that explains how an individual's thoughts and actions continually interact to change their behavior. The theory is well aligned with the proposed enhanced strategies which focus on reinforcing the intervention content to improve the participants' behavioral capability and self-efficacy to adhere to the intervention.

All participants in both groups will receive the DPP-GLB once per week for 12 weeks, then twice monthly for 12 weeks (18 sessions total). The sessions will be delivered by trained community members online eg. UK-Zoom and each session will last 1 hour. The Community Health Workers (CHWs) will be adult community members with at least a high school education. They will receive 16 hours of training on intervention delivery and on human subjects research with materials from the Community Involvement in Research Training (CIRT) developed by the University of Illinois at Chicago Center for Clinical and Translational Science. The CHWs will be added as Study Personnel in this protocol as they are identified and trained.

The intervention was developed by the University of Pittsburgh Diabetes Prevention Support Center (DPSC) which is periodically updated to reflect current dietary and PA recommendations. The DPP-GLB maintains the DPP program goals to achieve a 7% weight loss and to progress participants to 150 minutes per week of moderately intense PA by 6 months. The entire DPP-GLB program and related materials are accessible online through the University of Pittsburgh DPSC (Diabetes Prevention Support Center) and has been approved by the CDC for application to the CDC Diabetes Prevention Recognition Program. The manual and materials are available to the general public and available at the University of Pittsburgh website; [www.diabetesprevention.pitt.edu/index.php/group-lifestylebalance-materials/](http://www.diabetesprevention.pitt.edu/index.php/group-lifestylebalance-materials/)

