The DPP-GLB program has been rigorously tested in diverse community settings, including by the PI in churches, and shown to lead to clinically meaningful weight loss. For the purpose of this study and the focus on early loss weight response adherence we will deliver the intervention online e.g. UK-Zoom in 18 sessions (1 weekly x 12 weeks then twice monthly x 12 weeks) with the goal of losing 5% of body weight from baseline up to 3 months and to increase physical activity to 150 minutes per week. Participants in both groups will receive the same dose of the intervention (18 sessions) in 1-hour long group-based sessions delivered online eg. UK-Zoom once weekly for 12 weeks followed by six group-based sessions delivered twice monthly for 1 hour. The participants will receive supportive materials such as a weekly food diary and a FitBit/pedometer. Team members will deliver all participant study materials to the church/site for distribution to each participant.

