## CT Gov analysis plan

We analyzed study data descriptively, via means and standard deviations (SD) or frequency distributions, both as a summary of variables at each time point and as a check for missing and out-of-range values. We used T-tests and Chi Square tests of association to make baseline demographic comparisons between the treatment and comparison groups and between those who completed the study and those who were retained in the analytic sample but were missing one or both follow-up weights at 12 and 24 weeks. We evaluated means, SD, and Pearson product moment correlations among the variables indicating percent weight loss at 4, 12, and 24 weeks, with percentage of classes attended, and for the treatment group nonresponders the number of completed CHW calls.

We accounted for the cluster-randomized design and used repeated measures mixed modeling to evaluate the percent decrease in weight over *Time* (timepoints of 4 weeks, 12 weeks, and 24 weeks, relative to weight at baseline), between *Intervention Conditions* (Treatment vs. Comparison), and by *Response status* (responder vs. nonresponse). In addition to these main effects, we included the two- and three-way interaction terms. We included covariates that had the largest observed differences between the Treatment vs. Comparison group and/or those who completed the study versus those who missed one or both 12 and 24-week data collections. We evaluated post-hoc pairwise differences using Fisher's least significant difference procedure for pre-planned comparisons. The data analysis was done using SAS, v. 9.4; an alpha level of .05 was used for inferential testing.

For the cost effectiveness analysis we evaluated the cost of the intervention arm by comparing the incremental cost and weight loss with the active control arm (Aim 3). We compared the cost and outcomes associated with the intervention arm relative to the active control arm by calculating ICERs. An ICER is the ratio of the incremental change in costs divided by the incremental change in outcomes. Our primary cost effectiveness analysis focused on incremental cost per kilogram (kg) lost.

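### The analysis plan names no primary test for the nonresponder hypothesis at 3 months, and Fisher's LSD at .05 with no stated gate lets an arm difference at either 12 or 24 weeks be claimed

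*Combined protocol and SAP*

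**What the plan says.** The only directional hypothesis is in the protocol's Background: "We hypothesize that changes between baseline and 3 months will be more pronounced among the nonresponders in the intervention group", compared with nonresponders in the active control group.

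Objective 1 (Objectives) fixes the outcome and the contrast but not the time: "To evaluate differences over time in the primary outcome of weight", between nonresponders in the two arms.

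Other time references differ. The DPP-GLB section describes delivery in this study "with the goal of losing 5% of body weight from baseline up to 3 months". The same section gives the curriculum's own aims, "to achieve a 7% weight loss and to progress participants to 150 minutes per week of moderately intense PA by 6 months". Objective 2 concerns mediators and moderators of the "relationship between intervention status and weight loss response at 6 months in both nonresponders and responders". Study Design plans to "enroll and follow-up 500 participants over a period of 6 months".

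The CT Gov analysis plan models percent weight decrease at 4, 12 and 24 weeks by Condition and Response status, with all interactions. It evaluates what it calls post-hoc pairwise differences by Fisher's "least significant difference procedure for pre-planned comparisons", and "an alpha level of .05 was used for inferential testing". It does not list the comparisons, name a leading contrast or time point, require an omnibus test first, or give an adjustment. It uses the word primary only for the cost-effectiveness analysis. It is written in the past tense.

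**The concern.** The protocol supplies a hypothesis with a population, a contrast and a time. The analysis plan never refers to it. A reader of the results cannot tell which p-value was meant to decide the nonresponder question, because the same tests are called both post-hoc and pre-planned and are not enumerated.

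Two contrasts are natural candidates: nonresponders by arm at 12 weeks and at 24 weeks. With LSD at .05 and no stated condition, a null result on the 3-month hypothesis with p below .05 at 24 weeks could be reported as the trial's positive finding, and so could the reverse. The rule as stated does not hold the stated .05 across those two chances.

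**Working it through.** **Plan's own figure.** The plan states only the alpha of .05. It gives no family-wise error rate, power calculation or effect size to reproduce. One test at .05 has error .05, so the question is what happens with two.

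**Inputs.** Two nonresponder arm contrasts, at 12 and 24 weeks (CT Gov analysis plan). Each is tested at .05, taken as two-sided because the plan does not say (critical value 1.960). The correlation rho between the two test statistics is not in the documents. I vary it from 0 to 0.9 as an assumption.

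**Error with no gate and no arm effect.** P(either) = .05 + .05 − P(both), with P(both) from the bivariate normal. P(24 weeks only) = P(either) − .05. The last column requires a joint 2-df test of the two contrasts first (chi-square above 5.991). It is simulated and hypothetical, since the plan specifies no such test.

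| rho | P(both) | P(either) | 24 weeks only | Either, behind joint 2-df gate |
|---|---|---|---|---|
| 0 | 0.25% | 9.75% | 4.75% | 4.7% |
| 0.5 | 0.93% | 9.07% | 4.07% | 4.2% |
| 0.7 | 1.65% | 8.35% | 3.35% | 3.7% |
| 0.8 | 2.19% | 7.81% | 2.81% | 3.5% |
| 0.9 | 2.96% | 7.04% | 2.04% | 3.2% |

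At rho 0 this is 1 − 0.95² = 9.75%. Using 18 degrees of freedom (20 sites − 2) instead of the normal changes the range little: 6.9% to 9.6%.

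**One designated test.** A single primary contrast at 12 weeks has error 5% whatever rho is.

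**Holm over the two contrasts.** The smaller p-value is tested at .025 (critical value 2.241). If it passes, the larger is tested at .05. Error is at most 5%; in simulation it is 4.6% at rho 0.5 and 3.6% at rho 0.9. For power, assume each test alone would have 80%, so the mean shift is 1.960 + 0.842 = 2.802.
- Effect at one time only: P(Z > 2.241 − 2.802) = P(Z > −0.561), about 71%.
- Effects at both times, rho 0.5 to 0.9: about 75% to 77% at each time (simulation).

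**A strict sequence, 12 weeks then 24 weeks.** This also holds 5%. Under the same assumptions, an effect present only at 24 weeks would be claimed about 3% of the time (2.5% to 3.4% for rho 0.9 to 0.5). The enhanced calls are weekly from week 5 (section 2.b) to a maximum of 20 (Payment). Weeks 5 to 12 hold 8 calls, so about 8/20 = 40% of the contacts precede the 12-week weight.

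**The case against.** **LSD is classically protected.** Fisher's procedure is usually run after a significant omnibus test, and the plan describes the model effects before the pairwise differences. A reader might infer from the text that LSD was run without protection. The documents do not show that; they only fail to state a gate. With a joint gate the error would be about 3.2% to 4.7%. This stands, and it makes the inflation conditional. It does not say which time point leads.

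**The model already carries Objective 1.** It does: the hypothesized contrast can be estimated from the three-way model at each time. A reader might infer that the model cannot test the hypothesis, and that would be wrong. The gap is in designation and error control.

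**The time-point conflict is thin.** A reader might infer that the documents set up 6 months as a rival primary time point. The support is weak: the 6-month weight goal belongs to the curriculum, and Objective 2 is a mediator and moderator aim. The real ambiguity is that Objective 1 names no time. The Background sentence, for its part, does not name weight, so a 12-week primary combines the two passages.

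**It is called a pilot, and the analysis may be done.** Objectives uses the word pilot, but Background aims to establish efficacy, in 500 participants at 20 sites. The past tense is a fair point: a designation made now cannot restore pre-specification. It can only be disclosed as such.

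**Sixty-six comparisons.** The model has 3 × 2 × 2 = 12 cells and hence 12 × 11 / 2 = 66 pairwise differences. A reader might infer uncontrolled testing on that scale. The plan limits itself to a pre-planned set, so that is not supported. The attachments, including the amendment letters, were not available and might list the set.

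**Conclusion.** The concern holds in a limited form. The analysis plan does not turn the protocol's 3-month nonresponder hypothesis into a designated primary test, and its stated rule allows a claim at either 12 or 24 weeks.

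If no gate was applied and there is no arm effect, the chance of at least one false claim is 7.0% to 9.75%, against the nominal 5%. This assumes two-sided tests and a between-time correlation of 0.9 down to 0. The excess of 2.0 to 4.75 points is modest. The larger consequence is interpretive: the time point that decides the trial's conclusion can be settled after the results are seen. Nothing in the documents shows that this happened.

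Making 24 weeks depend on significance at 12 weeks is not needed, and it fits poorly with a call schedule that runs mostly after week 12.

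**What to change.** 1. Designate the Condition difference in percent weight change among nonresponders at 12 weeks as the primary test, two-sided .05, citing the Background hypothesis. Name that time point in Objective 1 as well as in the analysis plan.
2. Report the 24-week nonresponder contrast alongside it as secondary, with a confidence interval, whatever the 12-week result. Do not require significance at 12 weeks first.
3. List the pre-planned comparisons. Report all other pairwise differences as exploratory estimates with confidence intervals, not as LSD significance claims.
4. If the sponsor reads Objective 1 as giving 12 and 24 weeks equal standing, apply Holm across those two contrasts in place of LSD.
5. If the analysis is complete, keep LSD in the account of what was done and state whether an omnibus test was required first. Disclose that the designation comes from the protocol hypothesis and not from the analysis plan.

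**Cost.** Wording and relabelling only; no new data. With a 12-week primary, a difference seen only at 24 weeks becomes a secondary finding. Under Holm, and on the 80% illustration above, power falls by about 3 to 5 points at each time with effects at both, and by about 9 points for an effect at one time only.

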### Overview of DPP-GLB Intervention:

#### Schedule Participant Handouts and Leader Guides

##### Month 1

Session 1: Welcome to the Diabetes Prevention Program Group Lifestyle Balance

Session 2: Be a Calorie Detective

Session 3: Healthy Eating

Session 4: Move Those Muscles

##### Month 2

Session 5: Tip the Calorie Balance

Session 6: Take Charge of What's Around You

Session 7: Problem Solving

Session 8: Step Up Your Physical Activity Plan

##### Month 3

Session 9: Manage Slips and Self-defeating Thoughts

Session 10: Four Keys to Healthy Eating Out

Session 11: Make Social Cues Work for You

Session 12: Ways to Stay Motivate

Sessions 13-18 will reinforce content introduced in sessions 1-12.

After the participants have attended four sessions, we will identify nonresponders (defined as less than or equal to 1% weight loss) by weighing all participants. Both groups including the nonresponders will continue with the group sessions, however additionally, the nonresponders in the enhanced intervention sites will receive the individual-level enhanced intervention for the duration of the intervention which includes weekly telephone support.

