## 2) DPP-GLB Enhanced Intervention Program (including telephone support)

### 2.a. Identification of Nonresponders:

At session four, the research data collector team member will weigh participants and calculate the percentage of weight loss. We will use percentage of weight loss rather than pounds because percentage is more applicable to a wide weight range and is consistent with the recommendations of the Obesity Society clinical guidelines. Participants who have lost less than or equal to 1% of their weight by 4 weeks will be defined as nonresponders and will remain nonresponders regardless of subsequent weight response. The nonresponders in both groups will continue with the standard DPP-GLB group-based intervention, however the nonresponders at the intervention sites will also receive the enhanced intervention delivered through weekly telephone support.

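### The cost-effectiveness result is planned as a whole-arm ratio with no measure of uncertainty and no allowance for clustering, although its kilogram denominator may be imprecise enough to fall near or below zero

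*Combined protocol and SAP*

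**What the plan says.** The Objectives section words Objective 3 as a comparison of whole arms: "Conduct a cost effectiveness analysis to evaluate the cost of the intervention arm by comparing the incremental cost and weight loss with the active control". The CT Gov analysis plan repeats this: "We compared the cost and outcomes associated with the intervention arm relative to the active control arm by calculating ICERs". It then defines the measure: "An ICER is the ratio of the incremental change in costs divided by the incremental change in outcomes". It adds: "Our primary cost effectiveness analysis focused on incremental cost per kilogram (kg) lost". These sentences are the whole stated method. They name no interval, bootstrap, net benefit, acceptability curve or sensitivity analysis.

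The same plan says that the cluster-randomized design was accounted for, but in the sentence on the mixed model of percent weight decrease. Nothing carries that over to the ratio.

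The added care goes to part of one arm. The section on identifying nonresponders says that "the nonresponders at the intervention sites will also receive the enhanced intervention delivered through weekly telephone support". Tailored videos follow from those calls, and the Payment section gives these participants $5 per completed call, up to $100. Both arms are planned to have the same 18 group sessions. Objective 1, by contrast, compares weight "between nonresponders in the intervention group compared to nonresponders in the active control group".

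**The concern.** A cost-per-kilogram figure can be read only if the kilogram difference beneath it is clearly away from zero. The added cost is almost certainly positive, so the sign of the ratio depends on the weight difference. When that difference is close to zero, the ratio becomes very large. When it is negative, the ratio no longer means cost per kilogram lost. A ratio reported alone shows the reader neither problem.

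The design makes a small denominator plausible. Responders are planned to have the same care in both arms, so they may contribute variation to the whole-arm weight difference without contributing signal. Sites were randomized, so the variation between sites belongs in the uncertainty too. At stake is Objective 3: a single figure could be taken as a firm price per kilogram for a community program when the data support no such precision.

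**Working it through.** **Figures in the plan.** There is no power calculation, SD, ICC, effect size, dropout rate or cost figure to reproduce. The layout is consistent: 20 sites x 25 = 500, which is 10 sites and 250 participants per arm (Study Population; Study Design; Subject Recruitment Methods).

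**Assumed inputs, none given in the documents.** SD of weight change 5 kg; ICC 0.01-0.03; nonresponder share p = 0.3-0.5 under the week-4 rule; true effect in nonresponders d = 1-2 kg, with 3 kg as a contrast; no effect and no added cost in responders; equal site sizes; no dropout. The nearest figure in the documents is the 40-60% in the Background who miss the overall weight goal, which is a different definition.

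**Step 1: is the ratio biased?** With added cost c per nonresponder, the whole-arm ratio is (p x c)/(p x d) = c/d. The share cancels, so dilution does not change the target.

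**Step 2: precision of the whole-arm denominator.** SE = sqrt[2 x 25/250 x (1 + 24 x ICC)], where the second 25 is SD squared.

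- ICC 0.01: sqrt(0.20 x 1.24) = 0.50 kg
- ICC 0.03: sqrt(0.20 x 1.72) = 0.59 kg

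**Step 3: chance of a zero or negative denominator.** This is Phi(-p x d/SE).

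| p | d (kg) | whole-arm difference (kg) | ICC 0.01 | ICC 0.03 |
|---|---|---|---|---|
| 0.3 | 1.0 | 0.30 | 27% | 30% |
| 0.4 | 1.5 | 0.60 | 11% | 15% |
| 0.5 | 2.0 | 1.00 | 2% | 4% |
| 0.3 | 3.0 | 0.90 | 4% | 6% |
| 0.5 | 3.0 | 1.50 | 0.1% | 0.5% |

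In the middle case (p = 0.4, d = 1.5) the whole-arm difference is 0.60/0.50 = 1.2 or 0.60/0.59 = 1.0 standard errors from zero. At that expected value a 95% Fieller interval for the ratio is unbounded.

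**Step 4: does restricting to nonresponders cure it?** SE = sqrt[2 x 25/(250p) x (1 + (25p - 1) x ICC)]. For p = 0.4 this is sqrt(0.50 x 1.09) = 0.74 kg or sqrt(0.50 x 1.27) = 0.80 kg. A 1.5 kg effect is then 2.03 or 1.88 standard errors from zero, and the chance of a zero or negative denominator is 2-3%. Over the grid with d = 1-2 kg it is 0.1-13%. The risk is lower, but the second value is below 1.96, and both are below the t critical value of 2.10 on 18 degrees of freedom (20 sites less 2). The ratio needs an uncertainty method in either population.

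**Step 5: a wider grid.** With p = 0.4-0.6, d = 1-3 kg, SD 4-6 kg, ICC 0-0.05 and retention 80-100%, the whole-arm risk runs from about 0% to 31.7%.

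**The case against.** The strongest reply is that the planned population is the right one. The whole-arm contrast is the randomized comparison, it is what Objective 3 asks for, and it answers the policy question of what adopting the enhanced program costs per kilogram. Nonresponse is determined at week 4, after sites are randomized, although before the calls begin at week 5. Zero effect in responders is also only an assumption. Community Health Workers both lead the group sessions and make the calls, and participants share sites, so spillover is possible and only the whole-arm result would capture it. All of this stands.

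A reader might infer that the diluted denominator makes the ICER wrong, or that nonresponders should replace the whole arm as the primary economic population. The documents support neither. Step 1 shows that the target is unchanged, and Step 4 shows that restriction does not by itself make the ratio usable.

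It is also fair that the percentages rest on inputs from outside the documents, that this is the third objective of a self-described pilot, and that the plan is a short summary in the past tense that refers to ICERs in the plural. More than one ratio may therefore have been computed, and a fuller economic method may sit in material not included here. None of this supplies an interval, or a way to carry site clustering into the economic result.

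**Conclusion.** The point holds as one about missing uncertainty. That gap needs no assumption: the plan gives an ICER with no interval and no link to the cluster design. Its practical size does depend on assumptions. With an SD of 5 kg, ICC 0.01-0.03, a nonresponder share of 30-50% and a 1-2 kg effect confined to nonresponders, the whole-arm denominator has about a 2-30% chance of being zero or negative. With a 3 kg effect the figure is about 0.1-6%. Sites of unequal size (up to 50 are allowed) or dropout would raise these chances. The harm is instability, not bias, and it bears on Objective 3, not on the weight outcome in Objective 1.

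**What to change.** - Keep intervention arm versus active control arm as the primary cost-effectiveness comparison.
- Report the cost difference and the kilogram difference separately, each with a 95% interval from a bootstrap that resamples sites within arm and keeps each participant's cost and weight together.
- Present the joint uncertainty as incremental net benefit over a stated range of willingness to pay per kilogram, with an acceptability curve. The documents give no such range, so the sponsor must choose and justify one.
- Show the ICER only beside these results. Do not rely on a percentile interval for the ratio, which fails when the denominator can cross zero.
- Add the nonresponder-only result as a supplementary analysis, noting that nonresponse is defined after site randomization. If the analysis has already been run, label it as added afterwards.

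The cost is revised wording and some extra programming. Weight and cost are already in the outcome schedule, so no new data are needed. The downside is a result that looks less precise than a single figure. With 10 sites per arm the bootstrap intervals are themselves approximate, which should be stated.
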